9. RESEARCH METHODS

9.1 STUDY DESIGN

This is a non-interventional, single-country study based on existing data from medical records of patients in Korea National Health Insurance claim data & mortality data from the Bureau of Statistics from Jan 2005 to Apr 2016. This is a retrospective review study of nationwide cohort, which analyses the claims data of the entire Korean population.

In total, at least 10,000 eligible patients are planned to be enrolled to this study.

9.2 SETTING

The study will be conducted in a general practice setting, Korea National Health Insurance claim data & mortality data from the Bureau of Statistics, which includes computerized medical records of more than half million patients in South Korea. The maximal observation period will be from Jan 2005 to Apr 2016.

- Inclusion criteria
 - Diagnosed with COPD [**based on ICD-10 code(J43.x-44.x except J430), as the primary or within the fourth secondary diagnosis and initiated LAMA or ICS/LABA more than twice a year from Jan 1, 2005 to Apr 30 2016**].
 - Age >55 years old as of 2005 when enroll started
- Exclusion criteria
 - Prescription history with any long acting bronchodilator for maintenance therapy (the patient should be inhaler naïve) from 2002 to 2005.
 - Prescription history with ipratropium bromide
 - Prescription history with Leukotriene receptor antagonist(LTRA) or ICS
 - Prescription history of LABA/LAMA FDC
 - Patients with lung cancer, IPF, ILD or lung transplantation at the time of COPD diagnosis

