9.3.2 Outcomes

9.3.2.1 Primary outcomes

Primary endpoint

- Recorded pneumonia based on 1)ICD-10 code (J12.x-J18.x, J69.0, J84.9, B96.0, J85.1) AND 2) CPT code of chest x-ray(71045-71048) or chest CT(71250,71260,71270,G0297) AND 3) prescription of antibiotics for pneumonia in Korean Guideline) incidence rate per year
- Frequency rate of COPD exacerbation per year
 - Moderate exacerbation: recorded as when COPD patients visited outpatient clinics with an ICD-10 code of COPD and systemic steroid medication and/or antibiotics were prescribed (within the first year after initial prescription of inhalers)
 - Severe exacerbation: when COPD patients visited the emergency room or were admitted to hospital with an ICD-10 code of COPD(*due to COPD worsening*) and were prescribed systemic steroid medication and/or antibiotics (within the first year after initial prescription of inhalers)
- Time to start triple combination therapy ICS/LABA/LAMA)
 - Time to add LAMA in patients with using ICS/LABA or, time to add ICS/LABA in patients with using LAMA before.

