9.9.2 Identifying patients with COPD

The beginning of COPD symptoms cannot be determined from the utilized data sources, whereas date of diagnosis usually can be determined. Therefore, COPD patients were determined using COPD diagnostic code and a prescription for COPD medications

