9.12 BIAS

This study will include users of LAMA and ICS/LABA. Immortal time bias will be minimal, as the follow-up will begin at the initiation of drug use. Adherence to drug use will be unknown.

Comparing the outcomes between users of LAMA and ICS/LABA will decrease confounding by indication, as the comparison group will have a similar indication to drug use than the patients in the LAMA-exposed cohorts.

The compared sub-cohorts will be matched on the basis of PS. The PS will be computed on the basis of a wide range of covariates related to sociodemographic characteristics, history of exacerbation, other comorbidities, and prior/concomitant use of other drugs. The PS matching will decrease the systematic differences between the sub-cohorts and, thus, decrease confounding.

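### The inclusion rule lets a COPD code recorded after the first inhaler qualify a patient, so follow-up can begin before COPD and contain time with assured survival and no countable exacerbation

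*Combined protocol and SAP*

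**What the plan says.** - **Eligibility.** Section 9.2, repeated in the abstract, asks for a J43–J44 code (except J43.0) "as the primary or within the fourth secondary diagnosis and initiated LAMA or ICS/LABA more than twice a year", between 1 January 2005 and 30 April 2016. The two conditions are joined by a plain conjunction. Section 9.9.2 is no more specific: "COPD patients were determined using COPD diagnostic code and a prescription for COPD medications".
- **Time zero.** Section 9.12: "Immortal time bias will be minimal, as the follow-up will begin at the initiation of drug use".
- **Exacerbations (a primary outcome).** Under 9.3.2.1 a moderate event is recorded when patients "visited outpatient clinics with an ICD-10 code of COPD and systemic steroid medication and/or antibiotics were prescribed". A severe event is recorded when they "visited the emergency room or were admitted to hospital with an ICD-10 code of COPD", again with a steroid or antibiotic. Both are limited to events "within the first year after initial prescription of inhalers".
- **Asthma.** It is not an exclusion. It appears only as an item in the propensity score (9.7.1.1).
- **Exclusions.** Prior LTRA or ICS use is excluded without a reference date. Lung cancer, IPF, ILD and lung transplantation are judged at COPD diagnosis, not at the first inhaler.
- **Matching.** Section 9.7.1 matches on sex, age band, propensity score and time since COPD diagnosis, the last only where the database allows.

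**The concern.** The objective is outcomes after starting therapy in patients who have COPD. If the code may follow the first inhaler, entry to the cohort depends on something that happens after time zero. Three consequences follow for such a patient:

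- Death before the code would have kept the patient out, so the interval from first inhaler to code is immortal time in the mortality comparison.
- No exacerbation can be recorded in that interval, because both definitions need a COPD code.
- The lung cancer exclusion, tied to COPD diagnosis, is applied after follow-up has begun. It can remove people who developed a secondary outcome during follow-up.

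The reassurance in 9.12 that "the comparison group will have a similar indication to drug use than the patients in the LAMA-exposed cohorts" is also unavailable for time before COPD was diagnosed. Pneumonia is less directly affected: its definition needs no COPD code, so events before the code can count, although the person-time is not that of a coded COPD patient.

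**Working it through.** **1. Trace one patient through the rules.** First ICS/LABA in 2006, no earlier inhaler, LTRA or ICS; first COPD code in 2012; age and inhaler-count criteria met.

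- Code within the period: yes. Initiation within the period: yes. Inclusion criteria met.
- Follow-up starts in 2006 (9.12). The exacerbation window is the year after that (9.3.2.1). With no COPD code before 2012, the countable events are zero whatever happens clinically.
- Assured survival: 2012 − 2006 = 6 years.
- ICS exclusion: taken with no date at all it would empty the ICS/LABA arm, so some reference date must be meant. Judged at the first inhaler, the patient stays; judged at COPD diagnosis, the patient goes. The text allows either.

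**2. Effect on the first-year exacerbation ratio.** The plan has no figure on this point to reproduce. Its study size (2 × 5,000 = 10,000) is a feasibility estimate with no event rate or effect size. Let f be the share of an arm coded L years after the first inhaler, and m = min(L, 1). Assume late-coded patients otherwise have the same event rate. With a true ratio of 1.00, the observed ratio (ICS/LABA to LAMA) is (1 − f₁m)/(1 − f₀m), where f₁ is the ICS/LABA share and f₀ the LAMA share *after matching*. The documents give neither share nor the lag, so every row is an assumption.

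| f₁ (ICS/LABA) | f₀ (LAMA) | Lag L | Observed ratio |
|---|---|---|---|
| 10% | 10% | 1 year or more | 0.90/0.90 = 1.00 |
| 5% | 0% | 1 year or more | 0.95/1 = 0.95 |
| 10% | 2% | 1 year or more | 0.90/0.98 = 0.92 |
| 20% | 2% | 1 year or more | 0.80/0.98 = 0.82 |
| 10% | 0% | 0.5 year | 0.95/1 = 0.95 |
| 0% | 2% | 1 year or more | 1/0.98 = 1.02 |
| 2% | 10% | 1 year or more | 0.98/0.90 = 1.09 |

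Equal shares leave the ratio intact but understate the rate in both arms: by 10% in the first row.

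**3. If events are counted over all follow-up.** Section 9.7.2 uses the full observation period, as long as 11 years. With one arm affected, the ratio is 1 − fL/T over T years. For f = 10% and L = 2: 1 − 0.10 × 2/5 = 0.96 over 5 years, and 1 − 0.10 × 2/11 = 0.98 over 11 years. The same fraction describes mortality: 0.10 × 2/5 = 4% of that arm's person-time could contain no death.

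**4. Could a small imbalance matter at this size?** Take 5% affected in one arm only, 5,000 per arm, an assumed 0.5 exacerbations per patient-year, and a two-sided 5% level (assumed; the plan states 95% intervals). Events = 5,000 × 0.5 × (1 + 0.95) = 4,875. The expected z is √(4,875/4) × |ln 0.95| = 1.79. The chance of a falsely significant result is about 43% under a Poisson model. With negative binomial overdispersion of 1 to 2 it is 31% to 25%. With no imbalance it is 5%.

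**The case against.** A reader might infer that the plan builds in an 8% to 18% bias in favour of ICS/LABA, since asthma is a separate reason to receive ICS and asthma patients coded later would gather in that arm. The documents do not support this, for four reasons.

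- **Matching.** If negative values of time since diagnosis are kept, a late-coded ICS/LABA patient is paired with a similar LAMA patient or dropped, and the ratio returns to about 1.00. Asthma in the propensity score pushes the same way. So 0.92 and 0.82 apply only if unequal shares survive matching, for example because negative values are set to zero or missing.
- **The ICS/LTRA exclusion.** If judged at COPD diagnosis, it removes late-coded ICS/LABA starters but not late-coded LAMA starters. That would leave the problem mainly in the LAMA arm and reverse the direction.
- **Intent.** The objective in Section 8 speaks of starting therapy in COPD, and the propensity model is fitted to identified COPD patients. Both suggest diagnosis was meant to come first.
- **Text not seen.** The ENCePP checklist points to Section 9.7.3 for time-related bias and sensitivity analyses. That section is redacted, and handling there cannot be ruled out.

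The first two points stand against any claimed size or direction. None closes the gap itself. Matching on time since diagnosis is conditional on availability, and the text does not say what happens when the value is negative. Balancing asthma does not make earlier events countable. An objective is not a selection rule. A sensitivity analysis would not change who is in the main cohort. The deferral to an SAP in 9.3 concerns variable definitions, whereas eligibility is set in 9.2.

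**Conclusion.** The point holds as a gap in eligibility. As written, the rule can admit patients on a later diagnosis, with assured survival to the code and time in which a primary outcome cannot be recorded. The statement in 9.12 that immortal time bias is minimal is therefore not secured by starting follow-up at drug initiation.

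Neither size nor direction can be derived from the documents. They depend on three unknowns: the share of late-coded patients left in each arm after matching, the lag to the code, and whether exacerbations are counted in the first year or over all follow-up. The ratios from 0.82 to 1.09 above are illustrations for assumed shares, not estimates. The correction is worth making whichever arm is affected more, because it removes selection on future information from both.

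**What to change.** In 9.2 and the abstract:

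1. Require a first qualifying J43–J44 code (except J43.0), in the primary or up to fourth secondary position, on or before the date of the first LAMA or ICS/LABA prescription. Call that prescription date the index date.
2. Exclude patients coded only afterwards and report their number by arm.
3. Judge the ICS/LTRA history and the lung cancer, IPF, ILD and lung transplantation exclusions at the same index date.

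The order is what matters. A fixed lookback, such as 12 months, is not needed and would drop patients diagnosed earlier without a recent COPD claim. Moving the start of follow-up to the later of the two dates is not a good substitute, because it would bring in prevalent users.

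The cost is one or two sentences and one date condition in the selection code. Section 9.9.2 says the diagnosis date can usually be found, and the claims tables in Annex 3 carry disease codes and treatment dates. The cohort will be somewhat smaller. Reading the percentages in 9.5 as LAMA 26% and ICS/LABA 37%, the source has 200,000 × 26% = 52,000 and 200,000 × 37% = 74,000 users per year against a target of 5,000 per arm. Those counts precede the age, inhaler-naive, inhaler-count and matching filters, so the remaining margin should be checked in the data.

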		
‘LAMA+LABA+ICS’ combination) in COPD patients using LAMA and ICS/LABA
 
 - Comparison of health care utilization: Medical cost / No. of prescriptions, visits and hospitalizations - Expected adverse events after long term use of ICS : recurrence of TB and incidence of NTM lung disease - Comparison of all-cause mortality differences in COPD patients using LAMA and ICS/LABA 
Comparison of lung cancer incidence in COPD patients using LAMA and ICS/LABA
			
Study design:	Non-interventional, Single-country study based on existing data from medical records of COPD patients treated with LAMA or fixed dose combination of ICS/LABA				
Population:	
 • Inclusion criteria 
 - Diagnosed with COPD [based on ICD-10 code (J43.x-44.x except J430), as the primary or within the forth secondary diagnosis and initiated LAMA or ICS/LABA more than twice a year from Jan 1, 2005 to Apr 30 2016]. - Age>55 years old as of 2005 when enroll started • Exclusion criteria 
 - Prescription history with any long acting and short bronchodilator for maintenance therapy (the patient should be inhaler naïve) from 2002 to 2005 - Prescription history with Leukotriene receptor antagonist(LTRA) or ICS - Prescription history of LABA/LAMA FDC 
Patients with lung cancer, IPF, ILD or lung transplantation at the time of COPD diagnosis
				
Variables:	Detailed definitions of variables that will be derived for statistical analyses and summaries will be included in the Statistical Analysis Plan (SAP).				

Name of company: Boehringer Ingelheim			
Name of finished medicinal product: Spiriva® HandiHaler®, Respimat® (Tiotropium Bromide Monohydrate)			
Name of active ingredient: Tiotropium Bromide Monohydrate			
Protocol date: 3 Jun 2020	Study number: 0205-0542	Version/Revision: 1	Version/Revision date:
Data sources:	Korea National Health Insurance claim data & mortality data from the Bureau of Statistics from Jan 2005 to Apr 2016.		
Study size:	At least 10,000 total. At least 5,000 for each arm.		

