Data analysis:	All analyses will be performed with SAS and R. All variables will be summarized descriptively through displays of mean(\pm standard deviations), median, and ranges for continuous variables, and frequency distributions of categorical variables. To address the imbalance of potential confounders between LAMA ICS/LABA groups, we matched treatment groups using propensity scores estimated as by multiple logistic regression analysis based on age, sex, socioeconomic status, Charlson Comorbidity Index, and asthma, and history of COPD exacerbation. Cox proportional hazards regression analyses will be used to estimate hazard ratios (HRs) and 95% confidence intervals (95% CIs) for all outcomes. For (possibly) repeating events (such as exacerbation event) additionally a Poisson regression model will be fitted for the number of events (taking into account the matching). Detailed methodology for summary and statistical analyses of data in this study will be documented in an SAP.		
Milestones:	Start of data collection in 2020 April 15 End of data collection in 2020 Dec 31 Start of data analysis in 2021 Jan 1 End of data analysis in 2021 Dec 31 Final report of study results expected in 2022 Aug		

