9.7.1.1 Propensity score methodology

The propensity score will model the likelihood among COPD patients of receiving LAMA and ICS/LABA. The model for the propensity score will to the extent possible include the following elements:

- 1) Age and sex
- 2) Socioeconomic status (e.g. income, educational level, single living)
- 3) History of COPD exacerbation
- 4) Charlson Comorbidity Index
- 5) History of asthma

A logistic regression analysis will be performed on the identified COPD patients where treatment with LAMA and ICS/LABA groups is the dependent, dichotomous variable and the independent variables are listed above (age, sex and history of COPD exacerbation et al.). Based on this analysis, the propensity score is calculated for each patient. For subgroup analyses, PS matching and evaluation of its success, as presented below, will be re-done as covariate balance is not automatically maintained in sub-cohorts.

Smoking may be an important confounder in COPD but smoking status is usually not available in the databases at all. If smoking status is confirmed to be available, the data will be analysed with and without smoking status included in the model and the magnitude of the confounding effect assessed (sensitivity analysis).

PS matching will be done in a 1:1 ratio using the nearest-neighbor algorithm, using calipers of width equal to 0.2 of the standard deviation of the logit of the PS (matches of the main exposure sub-cohort and the comparator sub-cohort are formed if the caliper width is not exceeded for the logit of PS). For LAMA-exposed patient to ICS/LABA-exposed patients will be selected within the same matching interval of the propensity score. The distribution of propensity scores will be examined between LAMA-exposed and eligible ICS/LABA-exposed. In the matching procedure, matched comparator sub-cohort patients (ICS/LABA) will be removed from the pool of eligible patients among the comparator sub-cohort so that a matched patient is no longer available for consideration as a potential match for another exposed patient.

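### The inhaler-naive washout stops in 2005 while patients can start until April 2016, and the listed matching variables omit the prior drug use that section 9.12 says is included

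*Combined protocol and SAP*

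**What the plan says.** Section 9.2 (Setting) admits COPD patients who "initiated LAMA or ICS/LABA more than twice a year from Jan 1, 2005 to Apr 30 2016". It excludes "Prescription history with any long acting bronchodilator for maintenance therapy", on the ground that patients should be inhaler-naive, and dates that check "from 2002 to 2005". The abstract uses the same dates but a wider class: "Prescription history with any long acting and short bronchodilator for maintenance therapy". Section 9.2 also excludes a history of ipratropium, of LTRA or ICS, and of the LABA/LAMA fixed combination, all without dates. Lung cancer is an exclusion judged at COPD diagnosis.

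Section 9.12 (Bias) states that "the follow-up will begin at the initiation of drug use" and that the propensity score draws on "other comorbidities, and prior/concomitant use of other drugs". Section 9.7.1.1 introduces its list with "The model for the propensity score will to the extent possible include the following elements" and names age and sex, socioeconomic status, exacerbation history, Charlson index and asthma. The abstract gives the same set: "multiple logistic regression analysis based on age, sex, socioeconomic status, Charlson Comorbidity Index, and asthma, and history of COPD exacerbation".

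**The concern.** A new-user comparison needs the naive check to end at each patient's own first prescription. Here it ends on a calendar date at the beginning of an 11-year entry period. A patient treated with LABA alone in 2010 who starts a study drug in 2012 meets every written criterion.

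Prior LABA use may mark longer or more severe disease. If it differs between the arms after matching, it can confound exacerbation rate and time to triple therapy, both primary outcomes. The listed adjustment does not measure it, and section 9.12 gives the impression that it does.

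Lung cancer, a secondary outcome, has a related problem. A cancer first recorded between COPD diagnosis and start of treatment is not excluded and could be counted as incident.

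**Working it through.** **1. Calendar coverage of the washout** (dates from section 9.2)

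- Initiation window: 1 Jan 2005 to 30 Apr 2016 = 11 × 12 + 4 = 136 months = 11.33 years.
- Washout to end-2005: 136 − 12 = 124 months uncovered; 124/136 = 91%.
- Washout to end-2004: 136/136 = 100% uncovered.
- On the end-2005 reading, a patient starting on 30 Apr 2016 could have up to 124 months (10.3 years) of LABA-alone use that the rule does not see.
- The end-2005 reading has a second fault. A patient who starts a study drug during 2005 has a long-acting bronchodilator prescription inside the exclusion period and could be removed by the index drug itself.

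**2. Do the other exclusions close the gap?** The undated ones make sense only if read as before the start of treatment, since an ICS exclusion applied at any time would remove the ICS/LABA arm. On that favourable reading they cover ipratropium, LTRA, ICS and the LABA/LAMA combination. LABA alone, which section 9.5 lists as its own class, is not covered. Short-acting beta-agonist use after 2005 passes too. If the undated exclusions were also meant for 2002–2005, the gap is wider.

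**3. Adjustment variables side by side**

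| Place | Variables | Prior drug use? |
|---|---|---|
| Abstract, data analysis | age, sex, socioeconomic status, Charlson, asthma, exacerbation history | no |
| 9.3.3 | age, sex, exacerbation history, income or insurance | no |
| 9.7 | as in the abstract | no |
| 9.7.1 | sex, age band, years since diagnosis, propensity score | no |
| 9.7.1.1 | as in the abstract | no |
| 9.12 | sociodemographic, exacerbations, comorbidities, other drugs | yes |

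The committed adjustment for standardized differences above 0.1 in section 9.7.1.1 applies to propensity-score variables. If the score is built from the list in that section, an imbalance in prior drug use does not trigger it. Only the discretionary extra adjustments in 9.7.1.1 and 9.7.2 could pick it up, and neither names a drug variable.

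**4. Look-back available for a repaired rule**

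- Claims held from 1 Jan 2002: 3.0 years for a start on 1 Jan 2005 and 14.3 years for a start on 30 Apr 2016.
- Claims held only from Jan 2005 (the data start given in the abstract, 9.1 and 9.4): a full 1-year window loses starts in 2005, 12/136 = 9% of the initiation window. A full 3-year window loses starts in 2005–2007, 36/136 = 26%.

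**5. Scale of possible confounding (illustration; every input assumed).** With outcome risk ratio RR for prior LABA use and prevalences p1 (ICS/LABA) and p0 (LAMA), the unadjusted bias factor is [1 + p1(RR − 1)] / [1 + p0(RR − 1)].

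- RR 1.2, p1 5%, p0 2%: 1.010/1.004 = 1.006.
- RR 2.0, p1 20%, p0 5%: 1.20/1.05 = 1.14.
- RR 2.0, p1 5%, p0 20%: 1.05/1.20 = 0.88.

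The documents supply none of these inputs, so this shows only that the effect could be trivial or material, in either direction.

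**The case against.** The strongest reply is that the lead-in to the list in 9.7.1.1 does not call it exhaustive, that section 9.12 can be read as adding prior drug use to it, and that sections 9.3 and 9.7 defer detail to an SAP. That would make the point a matter of harmonising text. It does not hold. Section 9.7.1.1 goes on to say that the regression's independent variables are those listed above it, and no visible list names a drug. The deferral covers variable definitions and analysis methods; the eligibility dates in 9.2 are stated outright.

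Other parts of the reply do stand. The intent to enrol naive patients is plain. The rule is the same in both arms, so bias needs a between-arm difference that survives matching on years since diagnosis and on a score that includes exacerbation history and asthma. LABA alone may be rare. Section 9.9.4 already concedes residual confounding. None of this makes the written rule do what it intends.

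The lung cancer part is weaker. Incidence would ordinarily leave out earlier cases, and section 9.9.2 identifies COPD by a code plus a COPD prescription, which may shorten the gap between diagnosis and study drug. The section 9.5 list of COPD drugs includes non-study drugs, however, so the gap need not close, and section 9.3.2.2 does not say how a cancer recorded in it is treated.

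**Conclusion.** The concern holds and should be fixed before the cohort is built. As written, the washout does not cover 91% to 100% of the initiation window, and patients with LABA-alone use after 2005 enter as naive even when the undated exclusions are read favourably. The statement in 9.12 about prior drug use conflicts with every visible variable list.

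The percentages are calendar shares, not shares of patients. The number of prior users, the confounding left after matching and its direction cannot be determined from the documents. Redacted parts of section 9.7 are not judged.

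**What to change.** 1. Define index as the first LAMA or ICS/LABA prescription and apply every prescription-history exclusion to records before it. Choose all available look-back (unequal, 3.0 to 14.3 years by start date) or a fixed window, and say which. A fixed window of up to 3 years is open to every starter if 2002–2004 claims are held, but misses older use.
2. State that the history exclusions use no records after index. The prescription-count rules in 9.2 and 9.3.1, which do use later records, are a separate matter.
3. Add prior respiratory drug use, for any class not excluded, to the list in 9.7.1.1 and to the balance check there, so that it agrees with 9.12.
4. Confirm that 2002–2004 claims are in the extract, and reconcile this with the January 2005 data start in the abstract, 9.1 and 9.4.
5. Reconcile the bronchodilator exclusions: the abstract includes short-acting drugs as a class, section 9.2 names only ipratropium.
6. Apply the lung cancer exclusion up to index.

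The cost is protocol and SAP wording, one covariate derivable from the medication history described in 9.6, and a check on the data held. Some prior users will leave the cohort. If the early claims are missing, early starters are lost as well: 9% of the initiation window with a 1-year look-back, 26% with a 3-year one.
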